2.4 Part 3 Expansion Cohort

The expansion cohort segment of this study will consist of approximately 18 ES patients.

All patients in the expansion cohort will receive the RP2D of TK216 in conjunction with primary supportive care prophylaxis (e.g., with growth factors, antidiarrheals, antiemetics) for bone marrow and/or gastrointestinal toxicities. The first three patients will also receive vincristine intravenously on the first day of each treatment cycle, at a dose of 0.75 mg/m². If DLT (Table 2) is observed in 1 of 3 patients, an additional three patients will receive the same doses of TK216 and vincristine. If fewer than 1 of 6 patients experience DLT, then the remaining patients in the expansion cohort will receive the RP2D of TK216 plus vincristine given intravenously on the first day of each treatment cycle, at a dose of 1.5 mg/m² to a maximum of 2 mg/m² per dose. If DLT is observed in ≥2 of the first six

patients, then the dosing of vincristine and/or TK216 will be revised in consultation between the Investigators and the Sponsor.

If TK216 treatment has been well tolerated in Cycle 1 and 2, starting in Cycle 3 the duration of the TK216 infusion may be increased (e.g., from 14 to 17 or 14 to 24 days). If the longer infusion is well tolerated, the duration of the TK216 infusion may be increased further in subsequent cycles. There is no maximum treatment duration. If a longer infusion time is not well tolerated, the patient may remain on study, but receive a shorter duration of TK216 infusion in the next treatment cycle. The assessments noted for Days 8+/-1 and 15+/-1 in the Section 16.3 Schedule of Events (Schedule Escalation and Expansion Cohorts) should be performed every 7-8 days during longer infusions (Adverse events, Concomitant medications, Vital signs, Symptom driven physical exam, Hematology, Clinical chemistry, Coagulation, Urinalysis, and Plasma for PK assessment). A complete blood count (CBC with differential) should be obtained approximately half way between the weekly assessment at the study center or local laboratory.

In Part 3 dosing will follow the schedule for the RP2D selected. If TK216 treatment has been well tolerated in Cycles 1 and 2, starting in Cycle 3 the duration of the TK216 infusion may be increased, in consultation with the Sponsor.

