2.1 Drug Administration

TK216 will be administered intravenously by continuous infusion via a central venous catheter. Instructions on calculating the correct dose, as well as instructions on preparing the dosing solution will be provided in the Pharmacy Manual.

Vincristine is administered intravenously at a dose of 0.75 to 1.5 mg/m² up to a maximum dose of 2 mg.

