2.2 Part 1 Dose Escalation Segment

The starting daily dose level in the dose escalation segment will be 18 mg/m²/day.

A “3+3” patient enrollment scheme will be followed during the dose escalation. This segment will be performed in sequential cohorts of patients receiving TK216 intravenously by continuous infusion via a central venous catheter. Cycles will consist of treatment for 7 consecutive days followed by a 14-day rest period (Cycle = 21 days). If 2 of 3 patients experience a first-cycle DLT then accrual to the cohort will cease. If a first-cycle DLT is seen in one of the 3 patients in a cohort, that cohort will enroll an additional 3 patients. The dose escalation will continue until a first cycle DLT has been observed in 2 of 6 or 2 of 3 patients. DLT is defined as an adverse event occurring during the first cycle that is at least possibly related to TK216 and meets the DLT definition. When 0 of 3, or 1 of 6 patients in a cohort experience DLT, the dose will be escalated in the subsequent cohort.

Dose escalation will begin with an accelerated phase in which the dose will be doubled in successive cohorts of 3 patients until 1 patient experiences a first-cycle DLT (as defined in Table 1); or 2 patients experience similar AEs that are greater than or equal to grade 2 severity (greater than or equal to grade 3 severity for hematological AEs) which occur during the first cycle. A toxicity that is clearly and incontrovertibly unrelated to TK216 may be excluded in consultation with the medical monitor.

Once this predetermined toxicity level has been encountered, subsequent cohorts will dose escalate in 50% increments following review of AEs and discussion with the investigators. The dose level for newly enrolled patients will be assigned by Oncernal Therapeutics, Inc. at the time of registration.

Table 1 Dose Limiting Toxicity – Part 1 Dose Escalation Segment

Category	Criteria

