2.3 Part 2 Schedule Escalation Segment

Once the MTD for patients receiving TK216 by continuous infusion for seven days has been identified, the tolerability of longer infusion times will be determined.

This segment will also be performed in sequential cohorts of patients receiving TK216 intravenously by continuous infusion via a central venous catheter. A "3+3" patient enrollment scheme will be followed during the schedule escalation. If 2 of 3 patients experience a first-cycle DLT then accrual to the cohort will cease, and the subsequent cohort will receive TK216 at the next lower dose. If a first-cycle DLT is seen in one of the 3 patients in a cohort, that cohort will enroll an additional 3 patients. DLT is defined as an adverse event occurring during the first cycle that is at least possibly related to TK216 and meets the DLT definition for the schedule escalation segment (Table 2). When 0 of 3, or 1 of 6 patients in a cohort experience first cycle DLT, the dose will be escalated in the subsequent cohort.

The starting daily dose level in the schedule escalation segment will be the MTD determined in the Part 1 dose escalation segment as described in the previous section.

The first schedule escalation cohort will receive TK216 by continuous IV infusion for 10 days.

The selection of dose and schedule for subsequent cohorts will be made by the Investigators and Sponsor after evaluating the first cycle results of the previous cohort. The dose level for newly enrolled patients will be assigned by Oncternal Therapeutics, Inc. at the time of registration.

By way of illustration:

- If 0 of 3 or 1 of 6 patients in the first dose escalation experience first cycle DLT, the second schedule escalation cohort will receive TK216 by continuous IV infusion at the same dose for 14 days.
- If 2 or more patients in the first dose escalation experience first cycle DLT, the second schedule escalation cohort will receive TK216 by continuous IV infusion at the next lower dose for 10 days.

The same decision algorithm will be used to select the dose and schedule for the third and subsequent schedule escalation cohorts.

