9.3 Sample size calculation

The sample size for the Part 1 dose-escalation portion and Part 2 schedule-escalation portion of the study will be determined by the number of escalation steps and the required sample within cohort (3 or 6 patients). The sample size for the expansion phase will be chosen to assist in determining whether sufficient preliminary evidence of efficacy is seen to justify further study. If at least 4 of the total of 18 patients enrolled at the RP2D achieve a response or have stable disease for at least 3 months, the statistical basis of evidence will be satisfied. This schema will use a promising ORR/SD of 30% and an uninteresting ORR/SD of 10%, with a one-sided α -level of 0.10 and power of 80%. Note that durable stable disease of 30% is also a promising outcome.

The following table gives the probability of dose escalation as a function of the true DLT probability:

True Probability of DLT	0.05	0.1	0.2	0.3	0.4	0.5	0.6	0.7
Probability of Escalation	0.97	0.91	0.71	0.49	0.31	0.17	0.08	0.03

For Part 4 (Cohort 11), the sample size was chosen to support the primary objective of assessing clinical response in patients with relapsed or refractory ES (including patients with ESFT) to assist in determining whether sufficient preliminary evidence of efficacy is seen to justify further study.

With a hypothesized ORR of 25% and an unacceptable (null) ORR of 5%, a sample size of 21 patients achieves 80% power assuming a one-sided exact test and a one-sided α -level of 0.025. If at least 4 of the total 21 evaluable patients enrolled in the cohort achieve a response, the statistical basis of evidence will be satisfied.

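### Part 3 vincristine run-in (Section 2.4): the go-ahead cannot be met once six patients are treated, and exactly 1 DLT in 6 has no assigned action

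*Combined protocol and SAP*

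**What the plan says.** Section 2.4 describes a run-in at the start of the expansion cohort of approximately 18 patients. It has four parts:

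- **Start.** "The first three patients will also receive vincristine intravenously on the first day of each treatment cycle, at a dose of 0.75 mg/m²".
- **Expansion to six.** "If DLT (Table 2) is observed in 1 of 3 patients, an additional three patients will receive the same doses of TK216 and vincristine".
- **Go-ahead.** "If fewer than 1 of 6 patients experience DLT, then the remaining patients in the expansion cohort will receive" the RP2D of TK216 with vincristine at 1.5 mg/m².
- **Revise.** "If DLT is observed in ≥2 of the first six" patients, the vincristine dose, the TK216 dose or both are to be revised by the investigators and the sponsor.

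The two escalation segments word the corresponding rule differently. Section 2.2 (Part 1) says: "When 0 of 3, or 1 of 6 patients in a cohort experience DLT, the dose will be escalated in the subsequent cohort". Section 2.3 (Part 2) says: "When 0 of 3, or 1 of 6 patients in a cohort experience first cycle DLT, the dose will be escalated in the subsequent cohort". Section 2.4 takes its DLT definition from Table 2, the Part 2 table, but does not refer to either decision rule.

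Section 9.3 gives operating characteristics for escalation: "The following table gives the probability of dose escalation as a function of the true DLT probability". It gives none for the vincristine run-in.

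**The concern.** The second group of three is enrolled only after a DLT in the first group, so six treated patients always include at least one DLT. Fewer than one of six means none, and the go-ahead therefore cannot occur on the only path that leads to six patients. Exactly 1 of 6 is neither below one nor at two or more, so it has no branch. Yet it is the one favourable result that the added three patients can produce.

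The result 0 of 3 also has no sentence of its own, because the go-ahead is written only for six patients. Its meaning is not seriously in doubt, but it has to be inferred.

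The threshold decides whether vincristine doubles, from 0.75 to 1.5 mg/m², for the rest of a cohort that admits patients from age 10 (Section 3.1, criterion 11). After a six-patient run-in about 18 − 6 = 12 patients are still to be dosed. For them the plan would supply only the general range in Section 2.1: "Vincristine is administered intravenously at a dose of 0.75 to 1.5 mg/m² up to a maximum dose of 2 mg".

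**Working it through.** **Inputs.** The run-in rule comes from Section 2.4, the comparison rules from Sections 2.2 and 2.3, and the escalation probabilities from Section 9.3. The documents state no DLT rate for TK216 plus vincristine, so the true rate p is varied over the values tabulated in Section 9.3. DLTs are taken as independent between patients with a common p.

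**Paths under the rule as written**

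| First three | Next three | Total | Action in Section 2.4 |
|---|---|---|---|
| 0 | not enrolled | 0 of 3 | go-ahead by implication only |
| 1 | 0 | 1 of 6 | none |
| 1 | 1, 2 or 3 | 2, 3 or 4 of 6 | revise |
| 2 or 3 | not enrolled | 2 or 3 of 3 | revise (already two or more within the first six) |

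No path ends at 0 of 6. That result would require three more patients at 0.75 mg/m² after 0 of 3, which the text does not provide for, and even then 1 of 6 would have no action.

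**Formulas**

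- P(0 of 3) = (1−p)³
- P(1 of 6) = 3p(1−p)² × (1−p)³ = 3p(1−p)⁵
- P(2 or more of the first three) = 3p²(1−p) + p³
- P(1 of 3, then at least one more) = 3p(1−p)² × [1 − (1−p)³]

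Example at p = 0.2: 0.8³ = 0.512; 3 × 0.2 × 0.8⁵ = 0.197; 3 × 0.04 × 0.8 + 0.008 = 0.104; 0.384 × 0.488 = 0.187. These sum to 1.

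**The plan's own table first.** If 0 of 3 or 1 of 6 passes, the escalation probability is (1−p)³ + 3p(1−p)⁵. If only 0 of 3 passes, it is (1−p)³.

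| p | Section 9.3 | 0 of 3 or 1 of 6 | 0 of 3 only | P(1 of 6) |
|---|---|---|---|---|
| 0.05 | 0.97 | 0.973 | 0.857 | 0.116 |
| 0.1 | 0.91 | 0.906 | 0.729 | 0.177 |
| 0.2 | 0.71 | 0.709 | 0.512 | 0.197 |
| 0.3 | 0.49 | 0.494 | 0.343 | 0.151 |
| 0.4 | 0.31 | 0.309 | 0.216 | 0.093 |
| 0.5 | 0.17 | 0.172 | 0.125 | 0.047 |
| 0.6 | 0.08 | 0.082 | 0.064 | 0.018 |
| 0.7 | 0.03 | 0.032 | 0.027 | 0.005 |

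The first rule reproduces all eight stated values to two decimals. The second reproduces one (p = 0.7). Section 9.3 was therefore computed with 1 of 6 as a pass. It concerns dose escalation, so it supports that reading of the run-in without settling it.

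**Size of the gap.** The last column is the chance of reaching the unassigned outcome, and also the difference between the two readings in the chance of moving to 1.5 mg/m². Its derivative, 3(1−p)⁴(1−6p), is zero at p = 1/6, which gives the maximum 3 × (1/6) × (5/6)⁵ = 0.2009. Once the run-in has gone to six patients, the chance of ending at 1 of 6 is (1−p)³: 0.73, 0.51 and 0.34 at p = 0.1, 0.2 and 0.3.

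**The case against.** The best case on the other side is that this is a drafting slip, probably for fewer than two of six, whose intent can be recovered from Sections 2.2 and 2.3, and that little hangs on it. Several of the supporting points are sound:

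- Two or three DLTs in the first three patients are already two or more of the first six. Spelling that out is a clarification, not a repair.
- Section 2.3 lets an individual Part 2 patient who has completed Cycle 2 start vincristine at 0.75 mg/m² and go to 1.5 mg/m² at the next cycle, with no cohort DLT gate. The protocol thus accepts the same step, although after two cycles of TK216 rather than from Cycle 1. Section 2.6 adds patient-level rules for neuropathy, seizures and bilirubin. These limit the safety weight of the gap.
- The run-in is a pooled decision on one cohort, so 1 of 6 would most likely lead to a query to the sponsor. Nothing shows that sites would act on it separately.
- A stricter gate for a new combination is plausible, so the permissive reading should not be assumed.
- Part 3 may already be complete. The documents do not say.

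None of this gives 1 of 6 an action. Consultation is prescribed only from two DLTs upward, and the rules in Section 2.6 concern individual patients, not the cohort decision.

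**Conclusion.** The concern holds. As written, the go-ahead in Section 2.4 is impossible at six patients, exactly 1 of 6 has no action, and 0 of 3 passes only by implication. This follows from the wording alone and needs no assumed rate.

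Its size does rest on assumed DLT rates: 0.18, 0.20, 0.15 and 0.09 for 1 of 6 at true rates of 10%, 20%, 30% and 40%, and never above 0.20. The chance of moving to 1.5 mg/m² is 0.91, 0.71, 0.49 and 0.31 if 1 of 6 passes, against 0.73, 0.51, 0.34 and 0.22 if only 0 of 3 does. The effect is confined to the vincristine dose for the remaining patients, about 12 after a six-patient run-in. It does not touch alpha, power or sample size. It should be corrected because a dosing decision depends on this threshold.

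**What to change.** The sponsor should first confirm the intended rule, then state it for each outcome in Section 2.4.

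- **If the Part 1 and Part 2 rule is meant:** change the go-ahead condition to *0 of 3, or no more than 1 of 6, patients with a DLT*. For clarity, change the revise condition to *2 or more of the first three or of the first six*. This agrees with Sections 2.2 and 2.3 and with the table in Section 9.3.
- **If a stricter gate is meant:** state that 0 of 3 is the only go-ahead, and name the vincristine dose that follows 1 of 6.
- **If the run-in is already complete:** record which rule was applied.

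The cost is two phrases in Section 2.4, with no added patients, visits or procedures. If the change is made by protocol amendment, Section 8.3 requires written IRB/IEC approval before it is implemented.

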1.3 Part 3 Expansion Segment

The primary objective of the Part 3 expansion segment is ORR defined as Complete Response (CR) and Partial Response (PR) of the RP2D regimen of TK216 administered intravenously via continuous infusion through a central venous catheter in patients with relapsed or refractory ES. (includes patients with Ewing sarcoma family of tumors-ESFT). The RP2D regimen may include use of vincristine, a standard therapy for Ewing sarcoma.

Secondary objectives of the Expansion Cohort segment of the study are to assess:

- Progression-Free Survival (PFS) defined as time from first dose of TK216 to tumor progression or death due to any cause
- Overall Survival (OS) defined as time from first dose of TK216 to death due to any cause
- Duration of response (DOR) as defined from the first date a response is identified (either CR or PR) until the date of disease progression
- Disease Control (DC) defined as the proportion of patients with a confirmed Complete Response (CR), Partial Response (PR) or Stable Disease (SD)
- Duration of Disease Control defined as first date of disease control identified (either CR, PR or SD) until the date of progression
- Safety and tolerability of TK216 alone and combined with vincristine as characterized by Adverse Event type, severity, timing and relationship to study drug, as well as laboratory abnormalities
- Exploratory biomarker development to enable prediction of drug toxicity, tumor response and the mechanism(s) of acquired study drug resistance.
- Pharmacodynamics of TK216 on molecular targets in surrogate tissue
- Pharmacokinetics (PK) of TK216 alone and when combined with vincristine

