It is anticipated that 4 to 6 cohorts will be completed during the schedule escalation segment of this trial. With the concurrence of the investigators and the study sponsor, further testing may be performed in up to 12 additional patients per dose level to refine the estimation of the MTD and RP2D at intermediate dose levels or to define a higher MTD and RP2D while using Cycle 1 primary supportive care prophylaxis (e.g., with growth factors, antidiarrheals, antiemetics) for bone marrow and/or gastrointestinal toxicities.

The duration of cycles will be variable. Following the scheduled infusions of TK216, a rest period will begin. The next cycle for a patient may begin as soon as all the patient's toxicities attributed to TK216 have resolved to less than Grade 3, or are clinically tolerable Grade 3 toxicities.

Once a patient completes Cycle 2 of any schedule escalation cohort, vincristine can be administered on Day 1 of a subsequent cycle and on Day 1 of each subsequent cycle. The initial dose of vincristine on Day 1 of the starting cycle will be 0.75 mg/m² given via intravenous infusion prior to the initiation of the TK216 infusion. Subsequent doses beginning on Day 1 of the next cycle and beyond will be 1.5 mg/m² up to a maximum dose of 2 mg.

Additional cycles of therapy may be administered provided that the patient meets the following criteria on Day 1 of each cycle:

- ANC \geq 1,000/mm³
- Hemoglobin \geq 8.0 gm/dL (Blood transfusions are permitted.)
- Platelets \geq 50,000/mm³
- Non-hematologic toxicity(s) recovered to less than Grade 3, or are clinically tolerable Grade 3 toxicities
- In patients receiving vincristine, clinically tolerable neurotoxicity, and lack of seizure activity

A rest period of 14 days is required following the first cycle, but the rest period may be reduced following subsequent treatments if the above criteria are met.

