 - b. If ≥ 4 weeks has elapsed for radiation therapy (RT); ≥ 6 months must have elapsed if prior total body irradiation, craniospinal RT or if $> 50\%$ radiation of the pelvis; ≥ 6 weeks must have elapsed if other substantial bone marrow radiation. Patients who have received brain irradiation must have completed whole brain radiotherapy and/or gamma knife at least 4 weeks prior to enrollment. (Part 4)
7. Stem Cell Transplant or Rescue without TBI: No evidence of active graft vs. host disease and ≥ 3 months must have elapsed since transplant.

8. Patients with controlled asymptomatic CNS involvement are allowed (see Concomitant Medications). Patients not requiring steroids or requiring steroids at stable dose (≤ 4 mg/day dexamethasone or equivalent) for at least 2 weeks are eligible.
9. Resolution of all acute toxic effects (excluding alopecia) of any prior anti-cancer therapy to NCI CTCAE (Version 4.03) Grade ≤ 1 or to the baseline laboratory values as defined in the table below.
10. Eastern Cooperative Oncology Group (ECOG) performance status (PS) ≤ 2 in patients ≥ 17 years old; or Karnofsky/Lansky > 50 in patients ≤ 16 years old.
11. Age
 - a. Patients age ≥ 18 years old (Cohort 1)
 - b. Patients must be ≥ 12 years old (Cohorts 2-5)
 - c. Patients must be ≥ 10 years old (Cohorts 6-10)
 - d. Patients must be ≥ 8 years old (Cohort 11)
12. Life expectancy of at least 3 months.

13. Baseline laboratory values fulfilling the following requirements:

Absolute Neutrophil Count (ANC)	$\geq 1000/\text{mm}^3$ ($\geq 1.0 \times 10^9/\text{L}$)
Platelets (PLT)	$\geq 100,000/\text{mm}^3$ ($\geq 100 \times 10^9/\text{L}$) (transfusion independent, defined as not receiving platelet transfusions within a 7 day period prior to screening)
Hemoglobin	$> 9.0 \text{ g/dL}$ (transfusions are allowed)
Serum Creatinine or Creatinine Clearance	$\leq 1.5 \times \text{ULN}$ $> 60 \text{ mL/min}$
Total Serum Bilirubin	$\leq 1.5 \times \text{ULN}$
Liver Transaminases (AST/ALT)	$\leq 2.5 \times \text{ULN}$; $\leq 5 \times \text{ULN}$ if liver metastases are present
Alkaline Phosphatase (ALP)	$\leq 2.5 \times \text{ULN}$; $\leq 5 \times \text{ULN}$ if liver and/or bone metastases are present
Serum calcium and potassium	Normal or \leq CTCAE Grade 1 with or without supplementation.
Pregnancy test if female of child-bearing potential	Negative within 7 days of starting treatment

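### Section 2.4 caps Part 3 vincristine at 2 mg/m², a limit that cannot bind at 1.5 mg/m² and that conflicts with the absolute 2 mg cap in sections 2.1 and 2.3

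*Combined protocol and SAP*

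**What the plan says.** Three sections of the combined protocol and SAP set a vincristine maximum.

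- **Section 2.1, Drug Administration**, not restricted to any Part: "Vincristine is administered intravenously at a dose of 0.75 to 1.5 mg/m² up to a maximum dose of 2 mg".
- **Section 2.3, Part 2 Schedule Escalation Segment**, for doses after the first: these "will be 1.5 mg/m² up to a maximum dose of 2 mg".
- **Section 2.4, Part 3 Expansion Cohort**, for patients treated after the initial toxicity check: vincristine "at a dose of 1.5 mg/m² to a maximum of 2 mg/m² per dose".

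Part 3 dosing is staged. Section 2.4 begins: "The first three patients will also receive vincristine intravenously on the first day of each treatment cycle, at a dose of 0.75 mg/m²". No maximum is attached to that step. If the dose-limiting toxicity (DLT) criterion is met, the remaining patients receive 1.5 mg/m². If two or more of the first six have a DLT, "then the dosing of vincristine and/or TK216 will be revised in consultation" between the investigators and the sponsor. Vincristine is not certain to be used at all: section 1.3 says "The RP2D regimen may include use of vincristine".

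The dose modification text in section 2.6 and the vincristine guidance in section 7.3.5 state no other maximum. Nothing in the protocol gives a reason for a different ceiling in Part 3 or says which section prevails if they disagree.

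**The concern.** The maximum in sections 2.1 and 2.3 is an absolute amount in mg. The maximum in section 2.4 scales with body size. A cap of 2 mg/m² on a fixed dose of 1.5 mg/m² does no work, so it is hard to read as a deliberate Part 3 rule. With two of three sections agreeing and no rationale given, a unit slip is the natural explanation.

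The stake is dosing safety. Section 2.4 is where a site would look for the Part 3 dose. It states its own maximum, so it gives the reader no prompt to look for another. A site following that line alone would exceed the 2 mg cap in larger patients on Day 1 of every cycle given at 1.5 mg/m². Two features of the plan add weight:

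- The Part 3 DLT check is made at 0.75 mg/m², and no separate check is stated at 1.5 mg/m².
- Part 2 gives the combination under the 2 mg cap, so no other section provides for more than 2 mg of vincristine with TK216.

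Section 2.6 also treats vincristine dose as safety-critical, with interruption or reduction rules for neuropathy, seizures and raised bilirubin.

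**Working it through.** There is no sample-size or error-rate figure to reproduce here. The check is dose arithmetic.

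**Inputs from the documents**

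- Part 3 higher dose: 1.5 mg/m², maximum written as 2 mg/m² (section 2.4).
- Part 3 starting dose: 0.75 mg/m² (section 2.4).
- Absolute cap: 2 mg (sections 2.1 and 2.3).
- Part 3 size: approximately 18 patients (section 2.4).
- Part 3 minimum age: 10 years, with no upper limit stated (section 3.1, criterion 11, Cohorts 6-10).

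**Input not in the documents:** BSA. The values below are assumptions for illustration.

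**Step 1. Can the section 2.4 limit ever bind?** Dose = 1.5 × BSA and limit = 2 × BSA, so limit/dose = 2/1.5 = 1.33 whatever the BSA. It never binds.

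**Step 2. Where do the two rules part?** The absolute cap binds when 1.5 × BSA > 2, that is BSA > 2/1.5 = 1.33 m². At the 0.75 mg/m² step it would bind only when BSA > 2/0.75 = 2.67 m². In practice the problem is confined to the 1.5 mg/m² step.

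**Step 3. How large is the difference?** Section 2.4 alone gives min(1.5, 2) × BSA = 1.5 × BSA. With the absolute cap the dose is min(1.5 × BSA, 2 mg).

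| Assumed BSA (m²) | Section 2.4 alone (mg) | With 2 mg cap (mg) | Excess (mg) | Excess (%) |
|---|---|---|---|---|
| 1.2 | 1.80 | 1.80 | 0 | 0 |
| 1.5 | 2.25 | 2.00 | 0.25 | 12.5 |
| 1.73 | 2.60 | 2.00 | 0.60 | 30 |
| 2.0 | 3.00 | 2.00 | 1.00 | 50 |

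**Step 4. How many patients could be affected?** The lower limit is 0: vincristine may not be in the regimen, the DLT check may fail, or every treated patient may have a BSA at or below 1.33 m². The upper limit depends on how the DLT check is read.

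- If the step up to 1.5 mg/m² follows 0 DLTs in 3 patients, 18 − 3 = 15 remain.
- If six patients must always be assessed first, as the stated criterion of fewer than 1 DLT in 6 literally suggests, 18 − 6 = 12 remain.

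Because enrolment starts at age 10, some patients may fall below the 1.33 m² threshold. The documents do not allow that share to be estimated.

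**The case against.** The strongest reply is that the cap already covers Part 3. Section 2.1 applies to the whole study, and giving the smaller of 1.5 × BSA and 2 mg satisfies both section 2.1 and section 2.4. On this view section 2.4 contains a redundant limit beside a binding one, and an overdose needs a site to read section 2.4 in isolation. The logic is right: a compliant dose exists, and a careful reader of the whole protocol would find it. But section 2.4 is the more specific instruction and carries its own maximum, and no precedence rule points back to section 2.1. A pharmacist working from it would have no reason to suspect a lower limit.

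Three further points can be made.

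- **Part 3 may no longer be enrolling.** Section 4.2.4 says that from protocol version 7.0 the regimen is TK216 175 mg/m² over 28 days, which is the Part 4 regimen. The text does not say that Part 3 is closed, so the line cannot be treated as inactive. In Part 4, section 2.5 allows vincristine after progression without giving a dose, so the 2 mg cap in section 2.1 governs there.
- **The upper count of 15 rests on one reading of the DLT check.** This stands; 12 is equally supportable. It changes only a conditional upper bound.
- **Clinical harm is not demonstrated.** This also stands. The documents give no toxicity data for doses above 2 mg, and the section 2.6 rules would limit continued dosing once toxicity appears. Those rules act after the event and do not replace a correct ceiling.

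**Conclusion.** The concern holds. As written, the Part 3 maximum in section 2.4 has the wrong unit, can never take effect, and disagrees with the 2 mg cap in sections 2.1 and 2.3. The two rules differ only above a BSA of 1.33 m². At assumed BSAs of 1.5 to 2.0 m², section 2.4 alone allows doses 12.5% to 50% above the cap.

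The arithmetic on the limit and the crossover needs no assumption. The size of the excess rests on assumed BSA values. Exposure of any patient requires that vincristine is part of the Part 3 regimen, that the DLT check is passed, that BSA exceeds 1.33 m², and that the site doses from section 2.4 without applying section 2.1. Nothing in the documents shows that any patient was overdosed. The Part 3 decision rule and the trial's sample sizes and error rates are unaffected. It still needs correcting, because it is an active dosing instruction for a neurotoxic drug in a cohort open to children.

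**What to change.** In section 2.4, change the unit of the vincristine maximum from mg/m² to mg, so that the line reads as 1.5 mg/m² with a maximum of 2 mg per dose, matching sections 2.1 and 2.3. The sponsor's clinical team should confirm that 2 mg is the intended limit for Part 3. The edit removes one unit from one line and requires no change to the design, sample size or analysis.
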